17.4.	PROTOCOL COMPLIANCE	34
17.5.	PARTICIPANT CONFIDENTIALITY	34
17.6.	INDEMNITY	34
17.7.	RECORD RETENTION	35
17.8.	COMPETING INTERESTS	35
18. D	DISSEMINATION/PUBLICATIONS	35
18.1.	PUBLICATION POLICY	35
18.2.	AUTHORSHIP POLICY	
18.3.	Data Sharing Statement	
19. R	REFERENCES	37

LIST OF ABBREVIATIONS

Abbreviation/	Full Wording
Acronym	
AE	Adverse Event
AR	Adverse Reaction
AREDS	Age-Related Eye Disease Study
BCVA	Best-Corrected Visual Acuity
BEAVRS	British and Eire Association of Vitreo-Retinal Surgeons
BHSCT	Belfast Health and Social Care Trust
CFI	Comparative Fit Index
CFIR	
	Consolidated Framework for Implementation Research
CI	Chief Investigator
CORDS	The Classification for the Reporting of Complications in Retinal Detachment
CDE	Surgical Trials'
CRF	Case Report Form
CS	Cortical Sclerosis
CTA	Clinical Trial Authorisation
CTIMP	Clinical Trial of an Investigational Medicinal Product
DMEC	Data Monitoring and Ethics Committee
DMP	Data Management Plan
eCRF	Electronic Case Report Form
EDI	Equality, Diversity and Inclusion
EQ-5D-5L	EuroQol - Five Dimension - Five Level
ERIC	Expert Recommendations for Implementing Change
GCP	Good Clinical Practice
ETDRS	Early Treatment Diabetic Retinopathy Study
GLM	General Linear Models
GP	General Practitioner
HEAP	Health Economic Analyses Plan
HES	Hospital Eye Services
HRA	Health Research Authority
HTA	Health Technology Assessment
ICH	International Conference of Harmonisation
ICF	Informed Consent Form
ISF	Investigator Site File
IMP	Investigational Medicinal Product
ISRCTN	International Standard Randomised Controlled Trial Number
LogMAR	Logarithm of the Minimum Angle of Resolution
LRT	Likelihood Ratio Test
MM	Millimetre(s)
ModRUM	Modular Resource Use Measure
MRC	Medical Research Council
NEI-VFQ-25	National Eye Institute Visual Function Questionnaire
NHS	National Health Service
NICTU	Northern Ireland Clinical Trials Unit
NIHR	National Institute for Health and Care Research
NS	Nuclear Sclerosis
OCT	Optical Coherence Tomography
PCO	Posterior Capsule Opacification
PI	Principal Investigator
PIL	Patient Information Leaflet
PIP	
PPI	Pillar Integration Process
	Participant and Public Involvement
PPIER	Patient and Public Involved in Eye Research
PSC	Posterior Subcapsular
PSS	Personal Social Services
PVR	Proliferative Vitreoretinopathy
PVR-C	Proliferative Vitreoretinopathy – Grade C
QALY	Quality Adjusted Life Years

Doc no: Page 6 of 38

QoL	Quality of Life
QUB	Queens University Belfast
RCT	Randomised Controlled Trial
REC	Research Ethics Committee
RMSEA	Root-Mean-Square Error of Approximation
RPE	Retinal Pigment Epithelium
RRD	Rhegmatogenous Retinal Detachment
SAE	Serious Adverse Event
SAP	Statistical Analysis Plan
SAR	Serious Adverse Reaction
SDV	Source Data Verification
SEM	Structural Equation Modelling
SmPC	Summary of Product Characteristic
SOP	Standard Operating Procedure
SWAT	Study Within a Trial
TFA	Theoretical Framework of Acceptability
TMF	Trial Master File
TMG	Trial Management Group
TSC	Trial Steering Committee
UK	United Kingdom
VFQ-UI	Visual Function Questionnaire Utility Index
YAG	Yttrium Aluminum Garnett

Key Secondary Outcomes	At 52 weeks (+/- 6 weeks) after surgery for all outcomes except *: - Primary anatomical success (proportion of eyes with an attached retina after one vitrectomy). - Final anatomical success (proportion of eyes with an attached retina after two or more vitrectomies). - Intraoperative complications (total number and by severity score). - Postoperative complications (total number and by severity score). - Number and type of surgeries performed. - Refractive error *(difference between aimed (sought) and obtained post-operative refraction at 12 weeks after surgery in the phaco-vitrectomy arm and 6-8 weeks post-cataract surgery,		

	if this takes place, as per standard of care, in the vitrectomy only arm).		
	 Proportion of participants with BCVA <69 letters 		
	 Proportion of participants with BCVA <34 letters. 		
	- Time to achieve 'best vision'.		
	 Change in BCVA from baseline over time. 		
	Health related quality of life using EuroQol-5 level (EQ-5D-5L)		
	 Vision-specific quality of life using the National Eye Institute Visual Function Questionnaire-25 (NEI VFQ-25). 		
	 Participant's experience, and acceptability of treatments. 		
	 Use of health and social care services and non-health care. 		
	– Safety		
	Inclusion criteria - Adults >50 years of age		
	 Non-highly myopic (< -6 diopters; ≤26.5 mm axial length) phakic RRD 		
	 Naive to previous vitreoretinal surgery Pars plana vitrectomy is planned to repair their RRD. 		
	- Fais plana videctorily is planned to repair their KKD.		
	Exclusion criteria		
	- Presence of a "formed/established cataract."		
Key Inclusion and Exclusion Criteria	A "formed/established cataract" is defined as a cataract that, based on the Age-Related Eye Disease Study (AREDS) Research Group, is graded as nuclear sclerosis of ≥3 and/or if there is an anterior cortical cataract and/or a subcapsular posterior cataract involving the visual axis.		
	– Pseudophakia or aphakia.		
	 High myopia (≥-6 diopters; >26.5 mm axial length). 		
	 Giant retinal tear (i.e. presence of one or more retinal tears of ≥3 clock hours in size) 		
	- Retinal dialysis		
	Inclusion in an investigational drug study		
	Declined consent for participation		
Countries of Recruitment	United Kingdom		
Study Setting	Hospital Eye Services		
Target Sample Size	276 participants		
	48 months		

3. ROLES AND RESPONSIBILITIES

3.1. Funder

The National Institute for Health and Care Research (NIHR) Health Technology Assessment (HTA) Programme is providing the research costs for the COMBAT study (Reference NIHR161891).

The funder has no role in the study design, data acquisition, analysis and interpretation, or manuscript preparation.

3.2. Contributorship

The Chief Investigator (CI) conceived the study. The CI planned the study design, which was finalised with input from all co-investigators, including the COMBAT Participant and Public Involvement (PPI) Group. The statisticians determined the sample size and planned the data analysis, with input from the CI and co-investigators. The statisticians will oversee the primary statistical analysis of the trial. The health economists planned and will conduct the cost-effectiveness evaluation. Experts on qualitative research and implementation science designed and will undertake and analyse the evaluation of participant experience and acceptability and implementation strategies. The CI is the grant holder and will oversee the management and conduct of the study.

3.3. Sponsor

Queen's University Belfast (QUB) will act as Sponsor and the CI will take overall responsibility for the conduct of the study. Separate agreements will be put in place between the Sponsor and each organisation that will undertake Sponsor-delegated duties in relation to the management of the study. The Sponsor will have no role in the collection, analysis, and interpretation of data, writing of the reports, or decisions to submit reports for publication.

3.4. Trial Oversight Committees

Trial Management Group (TMG)

A Trial Management Group (TMG) will be established and chaired by the CI. It will comprise the CI and representatives from the Northern Ireland Clinical Trials Unit (NICTU), and any other co-investigators who provide trial specific expertise as required at the time, including the chair of the COMBAT PPI. The TMG will meet face to face or online on a monthly basis and communicate between times via telephone or online meetings and emails, as needed. The roles and responsibilities of the TMG will be detailed in the TMG Charter. Meetings will be formally minuted and a list of actions recorded and stored in the Trial Master File (TMF). All day-to-day activity will be managed by the Trial Manager/Trial Co-ordinator, in consultation with the CI as needed, providing a streamlined approach for handling enquiries regarding the study and disseminating communications.

Trial Steering Committee (TSC)

A Trial Steering Committee (TSC) will be convened to provide oversight with respect to the conduct of the study on behalf of the Funder and Sponsor. The minimum quoracy for any TSC meeting to conduct business is 67% (two thirds) of the appointed independent membership. The TSC will have an independent chair. The TSC will include the CI, at least one public member and others with clinical expertise relevant to the study. Membership, role of the TSC and frequency of meetings will be listed in the TSC Charter. The TSC will take responsibility for monitoring and guiding overall progress, scientific standards, operational delivery and protecting the rights and safety of trial participants. Meetings will be formally minuted and the minutes will be stored in the TMF. Observers may be invited to attend TSC meetings, such as the Sponsor or Funder representatives or the Trial Manager to provide input on behalf of the NICTU.

Data Monitoring and Ethics Committee (DMEC)

An independent Data Monitoring and Ethics Committee (DMEC) will be convened, comprising two independent clinicians with experience in undertaking clinical trials and an independent statistician. The DMEC's overarching responsibility is to safeguard the interests of study participants, in particular with regard to safety, and assist and advise the TSC so as to protect the validity and credibility of the study. The membership, the role of the DMEC and the frequency of meetings will be listed in the DMEC Charter. The DMEC will meet to agree conduct and remit, which will be detailed in the DMEC Charter. Meetings will be formally minuted and the minutes will be stored in the TMF. Following recommendations from the DMEC, the TSC will decide what actions, if any, are required. It will be the

Doc no: Page 11 of 38 responsibility of the DMEC to inform the Sponsor if concerns exist about participant safety, following which the Sponsor will take appropriate action. If a trial extension and/or funding is required above the level originally requested, the independent DMEC may be asked by the CI, TSC, Sponsor or Funder to provide advice and, where appropriate, information on the data gathered to date in a way that will not compromise the trial.

User Involvement

Interpretation of trial results, dissemination, and implementation: The results of the COMBAT study will be interpreted with input from the COMBAT PPI Group. The TMG will consult with the PPI Group to identify strategies for dissemination and implementation of trial results. The implementation strategy developed in COMBAT will support the implementation of the findings into practice.

Identification of areas of future research: The COMBAT PPI Group will help the researchers to identify new areas of research, based on the findings of COMBAT.

4. BACKGROUND AND RATIONALE

4.1. Background Information

Rhegmatogenous retinal detachment (RRD) is the separation of the retina from the wall of the eye, where it is normally attached. It affects 10-18 people per 100,000 per year (1,2). Thus, in the UK, with a population of around 68 million (3) there are 6700-12,000 RRD per year.

RRD can lead to permanent central and peripheral vision loss (i.e. total blindness) if not treated in a timely manner. Vitrectomy is the most common surgery done for RRD (4,5). Retinal reattachment following one vitrectomy occurs in 80-88% of eyes, with 59-67% gaining vision above 0.3 LogMAR, which is the vision required to fulfil UK driving standards (4,5).

Data from the British and Eire Association of Vitreo-Retinal Surgeons (BEAVRS) showed that most patients with RRD are phakic; this means that they still have their natural lens (i.e. have not had cataract surgery) (5). Data from the BEAVRS database (unpublished, but accessible to the COMBAT

Doc no: Page 12 of 38 Protocol v1.0 Final 25.02.25 IRAS 338079

research group) showed that of 8436 vitrectomies done in non-high myopic phakic eyes out of 13,900 vitrectomies performed at several sites in the UK, only 10% combined vitrectomy with cataract surgery (called phacovitrectomy) at the time of the RRD repair. Of 664 phakic eyes with at least 12 months follow-up in which combined surgery was not performed at the time of RRD surgery, 320 (48%) were recorded to have a cataract or to have had it already removed within three months of the original vitrectomy. Only 20% of these eyes had their own clear natural lens at 12 months following vitrectomy. Therefore, phacovitrectomy is done in a minority of patients at the time of RRD repair; and many patients have either a cataract present or undergo separate cataract surgery soon after the RRD surgery.

Previous studies have shown the potential benefits of doing combined RRD and cataract surgery (6,7). If the cataract is removed when the RRD is repaired, the view of the back of the eye may be clearer, because the surgeon will see through the clear artificial lens. Furthermore, the purpose of the vitrectomy is to remove the vitreous, which is a gel-like structure that fills the back of the eye. The vitreous is involved in the occurrence of the RRD and, given that the vitreous is also present around the posterior part of the lens of the eye, removing the lens allows a more thorough removal of the vitreous. This has the potential to improve the anatomical outcome of the vitrectomy (i.e. reattachment of the retina) and reduce the number of surgeries required because there would be less need for reoperations (repeated vitrectomies) if the first vitrectomy fails to put the retina back in place. Phacovitrectomy would also obviate the need to do the cataract surgery at a later time following the vitrectomy. Adding a phaco to the vitrectomy will add approximately 8 minutes to the surgical time (7) but could save 6000 cataract surgeries per year to the NHS. Reducing the number of surgeries might benefit both patients and the NHS by reducing hospital admissions and clinical appointments, thereby reducing NHS costs, and increasing capacity to deal with more patients. Moreover, when cataract surgery is done after vitrectomy, the vitreous is no longer present and there is less support to the lens. This may make the cataract surgery more difficult and increase the risk of intraoperative complications (8).

However, some studies have suggested that postoperative inflammation (9), accumulation of fluid in the centre of the retina (called cystoid macular oedema) (10), epiretinal membrane formation (10), and posterior synechiae (adherence of the iris to the intraocular lens) (11) may be more frequent after phacovitrectomy. Calculation of the required artificial intraocular lens, which is used at the time of cataract surgery to replace the natural lens of the eye, may be less accurate when doing combined phacovitrectomy in eyes where the macula (i.e. the central retina) is detached (10). This is because the calculation of the intraocular lens requires measuring the length of the eye and this measurement is less accurate if the macula is detached. However, errors appear to depend on the technique used for this calculation (12). A less accurate measure of the intraocular lens would mean people may need glasses to improve their vision following surgery.

4.2. Rationale for the Study

Previous studies comparing vitrectomy with phacovitrectomy in people with RRD have been mostly retrospective and small, with numerous methodological weaknesses. None have addressed patient reported outcomes, patient views and acceptability for one surgery over the other, or costs.

Two systematic reviews of phacovitrectomy versus vitrectomy and subsequent cataract surgery have been published recently (13,14). Farahvash et al. (13) included studies in which vitrectomy or phacovitrectomy were used for a variety of retinal disorders, including RRD, macular hole, epiretinal membrane, and others. They included six retrospective before and after studies and one prospective study on RRD but no randomised trials. Results for the RRD group were not given separately. The Mirshahi et al. review (14) included studies specifically comparing surgeries in people with RRD. The review included five retrospective before and after studies, one study defined as a "quasi randomised" and one randomised trial. Only one of the studies included in the review by Mirshahi et al. was in the Farahvash et al. review. The randomised trial in Mirshahi et al. review [Mora et al. (15)] was a small poorly reported study with 59 patients (59 eyes) randomised to vitrectomy alone (n=29) or phacovitrectomy (n=30). Although not clearly stated, the trial seems to have been a non-inferiority trial with a non-inferiority margin of 10% or less between groups for the primary outcome (retinal reattachment with a single surgery at 6 months). However, a 10% difference in single surgery success on retinal re-attachment seems clinically important. The authors stated that, accepting a 5% type 1 error and 80% power, a sample size of 50 eyes would be needed to detect differences between groups in the primary outcome (15). Secondary outcomes included final best-corrected visual acuity (BCVA), intraocular pressure, central macular thickness, and progression of cataract in the vitrectomy only group. Mora et al. stated that all outcomes (primary and secondary) were assessed at 1 week

and 1, 3 and 6 months after surgery but do not report if patients and outcome assessors were masked to treatment allocation. The trial found no differences in any of the outcomes at six months post-surgery except progression of cataract in the vitrectomy group. Patient reported outcomes and patient experience and acceptability, intra and post-operative complications and costs were not systematically evaluated.

Authors of both recent systematic reviews (13,14) called for randomised trials to determine the best surgical approach for people with phakic RRD. COMBAT is such a trial and the need for it has been confirmed by the COMBAT PPI group who noted that people with RRD are currently unable to make an informed decision about whether to have vitrectomy alone or phacovitrectomy because of the lack of evidence about potential harms and benefits of each surgical approach. They confirmed that patients with RRD should be agreeable to joining COMBAT because both treatments have potential advantages and disadvantages. When they had their RRD, none of the patients in the COMBAT PPI group were offered a choice between having the surgeries at the same time or separately, with no discussion of the potential differences. COMBAT should provide the evidence to inform these discussions in the future.

4.3. Rationale for the Intervention

The intervention will be phacovitrectomy (i.e. phaco to remove the cataract and insert an intraocular lens and vitrectomy to repair the retinal detachment). This is performed routinely throughout the UK to treat people with a idiopathic macular hole. However, it is not the standard procedure for people with phakic, non-highly myopic RRD.

4.4. Rationale for the Comparator

The comparator in COMBAT is the current standard care (i.e. the performance of vitrectomy without concomitant cataract extraction) for most patients in the UK for whom vitrectomy is planned for the repair of the phakic, non-highly myopic retinal detachment, as shown by data from the BEAVRS database.

5. STUDY AIM AND OBJECTIVES

5.1. Research Hypothesis

We hypothesise that combined phacovitrectomy will be preferred by patients because it will provide faster visual recovery and obviate the need for a second surgery (the cataract surgery) following RRD repair, and possibly reduce the number of reoperations related to failure to re-attach the retina. The COMBAT PPI Group have highlighted that obviating the need for further cataract surgery should have a positive impact on patients because of the stress and anxiety that occurs before surgical procedures. Phacovitrectomy may reduce the number of visits and admissions to hospital, reducing costs and pressures on the NHS and probably reducing costs to patients such as travel costs and time off work for attending hospital visits. These costs are especially problematic for patients with limited income and the self-employed. Phacovitrectomy may also reduce other health inequalities because if cataract surgery is required after RRD repair, long waiting times for this surgery in the NHS could adversely affect people with lower income who may be unable to achieve visual rehabilitation as quickly as those with higher income who can afford to have their cataracts removed privately.

5.2. Research Question and Study Aim

Research question: In people with non-highly myopic phakic RRD (Population) in whom vitrectomy is planned to repair their RRD, is phacovitrectomy (Intervention) equivalent (equivalence margin +/- 7 ETDRS letters) to vitrectomy and subsequent cataract surgery (phacoemulsification) if/when needed (Comparator) for improving vision following surgery (primary Outcome) but superior for other (secondary) outcomes (listed below) in the 52 weeks (+/- 6 weeks) after surgery.

Aim: To conduct a pragmatic randomised trial evaluating clinical and cost-effectiveness, safety and acceptability and patient experience of combined phacovitrectomy versus vitrectomy and subsequent cataract surgery (if/when needed) for non-highly myopic phakic RRD and to undertake a structured

analysis of strategies to implement the phacovitrectomy pathway, if this is shown to be as good or better than current standard care.

5.3. Study Objectives

In people presenting with a phakic, non-highly myopic RRD, the objectives of the COMBAT study are;

- 1. To determine if the clinical effectiveness of phacovitrectomy is equivalent (or superior) to that of vitrectomy and subsequent cataract surgery (if/when needed).
- 2. To compare the cost-effectiveness of phacovitrectomy with that of vitrectomy and subsequent cataract surgery (if/when needed) via an economic evaluation.
- 3. To evaluate the participant experience and acceptability of phacovitrectomy compared with vitrectomy and subsequent cataract surgery (if/when needed) via a mixed methods evaluation.
- 4. To evaluate the post-trial implementation and scalability of phacovitrectomy via a process evaluation.

6. STUDY DESIGN

6.1. Study Design

Pragmatic, allocation-concealed, single-masked (outcome assessors), multicentre, randomised (1:1), equivalence trial with an internal pilot to assess feasibility of recruitment.

6.2. Internal Pilot

The internal pilot will take place during the first nine months of recruitment, to assess feasibility of recruitment and determine if the study should continue to a full trial. The go/amend/stop criteria will be assessed nine months after the first site is open to recruitment. The target recruitment will be an average of 0.5 participants per month per open site. With the proposed staggered opening of sites, the recruitment target for the internal pilot is 63 participants, which would represent 23% of the required sample size for the full trial.

Table 1 shows the criteria for progression to the full trial: GREEN: Progress to full trial. AMBER: Discuss feasibility with the TSC and NIHR and develop a recovery plan to reach the recruitment target, including evaluating options to improve recruitment and considering number of eligible patients identified, percentage of these patients randomised and reasons for non-randomisation, site recruitment performance, and recruitment procedures. RED: Decision to progress with trial will be made by the TSC and NIHR.

Table 1 Traffic light system for progression criteria from internal pilot to main study

Criteria (% threshold)	Red (<50%)	Amber (50-99%)	Green (100%)
Average recruitment rate/site/month	<0.25	0.25-0.49	0.5
Number of sites opened	<12	12 - 23	24
Number of participants recruited	<31	31 - 62	63

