14. STATISTICAL CONSIDERATIONS

14.1. Sample Size

COMBAT is powered to demonstrate treatment equivalence for the primary outcome. Based on two one-sided t-tests at the 2.5% significance level, a 15.2-letter standard deviation (27) and an equivalence margin of +/- 7 ETDRS letters (with a difference of 7 or fewer letters being considered not clinically meaningful) (28,29), 248 participants would be required to be 90% sure the 95% confidence interval will exclude a difference in means of more than 7 ETDRS letters. Allowing for 10% dropout, we will require a minimum of 276 participants. This sample size will be sufficient to detect a difference of 16% in the rate of retinal reattachment surgery between groups, which is clinically relevant.

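### Table 1 of the internal pilot puts a count of exactly 31 participants in Amber, although 31 of 63 is 49.2% and so Red under the table's own 50% rule

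*Protocol*

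**What the plan says.** Section 6.2 of the Protocol describes a nine-month internal pilot whose results decide whether the study goes on to the full trial. It states that "the recruitment target for the internal pilot is 63 participants", "which would represent 23% of the required sample size for the full trial". Table 1 sets three progression criteria against three colour columns. The column headings define the colours as percentages of target: Red under 50%, Amber 50 to 99%, Green 100%.

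The cells are:

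- Average recruitment rate per site per month: Red below 0.25, Amber 0.25 to 0.49, Green 0.5.
- Sites opened: Red below 12, Amber 12 to 23, Green 24.
- "Number of participants recruited": Red below 31, Amber 31 to 62, Green 63.

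The text above the table attaches an action to each colour. Green means progress. Amber reads "Discuss feasibility with the TSC and NIHR and develop a recovery plan to reach the recruitment target". Red reads "Decision to progress with trial will be made by the TSC and NIHR".

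**The concern.** The table states its rule twice, once as a percentage in the heading and once as a count in the cell. In the participant row the two do not agree at the Red/Amber boundary: the printed cut lets a result just under 50% of target count as Amber. A progression rule is fixed in advance so that nobody has to choose its reading after seeing the data. If the pilot closed on 31 participants, someone would have to decide whether the heading or the cell governs. The slip runs in the lenient direction, and the two colours carry different text: a recovery plan under Amber, a decision on whether to progress under Red.

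**Working it through.** **Inputs.** Pilot target 63 (section 6.2). Colour rule: Red under 50%, Amber 50–99%, Green 100% (Table 1 headings). Printed participant cells: Red below 31, Amber 31–62, Green 63 (Table 1). Full sample size 276 (section 14.1: "we will require a minimum of 276 participants").

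**The target itself.** 63/276 = 22.8%, which rounds to the stated 23%. The target is consistent with the full sample size and is not in question.

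**Where the printed 31 comes from.** 0.50 × 63 = 31.5. Rounding down gives 31, the lowest Amber count in the table, so the figure is explained by rounding.

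**Each count near the boundaries, as a share of 63:**

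| Count | Share of 63 | By column heading | By printed row |
|---|---|---|---|
| 30 | 47.6% | Red | Red |
| 31 | 49.2% | Red | Amber |
| 32 | 50.8% | Amber | Amber |
| 62 | 98.4% | Amber | Amber |
| 63 | 100% | Green | Green |

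The smallest whole number at or above 31.5 is 32. The heading and the row disagree at 31 and at no other count.

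**The other two rows, for comparison.** Rate: 0.25/0.5 = 50% exactly. Sites: 12/24 = 50% exactly. Both follow the heading, because half of each target is a value that can be printed as it stands. The participant target is odd, so its half is not a whole number, and rounding down moved the cut below 50%.

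**The case against.** The strongest reply is that this is rounding and no more. No whole number equals 31.5, the row prints explicit adjoining bands that can be applied as they stand, and the TSC and NIHR would see that 31 is within half a participant of the midpoint. Participant count is also only one of three criteria. All of this is fair, and it limits the point to an editorial one. It does not remove the conflict: section 6.2 does not say that the percentages are rounded or that the cells override the headings, and the other two rows follow the headings exactly.

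A reader might infer more than the Protocol supports, in four ways.

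- That the misprint could decide whether the trial stops. Section 6.2 sends both Amber and Red to the TSC and NIHR, and Red is a decision by those bodies, not an automatic stop. Section 6.4, which lists the grounds for premature stopping, names no pilot count.
- That the thresholds were agreed with the funder, so that the slip breaches an agreement. The Protocol does not say so. It gives NIHR a part in the Amber and Red steps, and section 3.1 says the funder has no role in study design.
- That landing on 31 is likely. The Protocol gives no basis for a probability. If the count is assumed to be Poisson, the chance of exactly 31 is about 7% with a mean of 31, about 0.6% with a mean of 45, and about 3 in a million at the planned 63. The first figure is a worst case.
- That the table has further gaps, because Green is printed as exact values and the rate row steps from 0.49 to 0.5. Any reader will take an above-target result as Green, and the step in the rate row is what a rate reported to two decimals looks like. Neither is an error.

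**Conclusion.** The point holds as a minor inconsistency. The participant row's Red/Amber cut in Table 1 departs from the table's own 50% rule at a single count, 31, which is 49.2% of 63. The finding rests only on reading the column headings as the rule, which the exact agreement of the other two rows supports. It matters only if the pilot finishes on exactly 31 participants. Even then the same two bodies consider the result, and the trial may continue under either colour. The planned 276 participants, the error rates and the primary analysis do not depend on it.

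**What to change.** In Table 1, print the participant row as Red below 32 (that is, 31 or fewer), Amber 32 to 62, Green 63 or more. The row then follows the same 50% rule as the other two, and the Red/Amber cut becomes stricter by one participant. If the trial team would rather keep 31 as the lowest Amber count, a note under the table saying that the printed counts take precedence over the rounded percentages would also leave only one reading. Either is a one-line correction with no effect on the design or analysis, best made before the pilot count is known.
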